#### **4 CHANGES IN THE CONDUCT OF THE STUDY OR PLANNED ANALYSIS**

There are no changes in the study conduct or analysis plans relative to the study protocol.

## **5        QUALITY CONTROL AND QUALITY ASSURANCE METHODS FOR DATA ANALYSIS**

Case report forms will be monitored and collected by ICON. All monitored eCRFs will be sent to the Data Management group at ICON and processed according to the ICON Study Specific Procedure SSP DM-45080001.01 Data Management Plan (DMP). The DMP describes eCRF data processing, edit checks, data query management, medical dictionary coding, SAE reconciliation, data transfers, and data quality review through database lock or any necessary reopening of the database. After database lock, the data will be retrieved from the database using SAS® 9.4 or higher version.

## **6 PHARMACOKINETIC AND EFFICACY ASSESSMENTS**

### **6.1 Pharmacokinetic Assessments**

#### **6.1.1 Pharmacokinetic Analysis**

Pharmacokinetic analyses will be based on the PK population.

Plasma PK concentrations for the investigational product will be presented in a data listing and summarized in tabular and graphical formats, as data allow. Overlay individual concentration-time plasma PK profiles may also be presented.

Population PK analysis using non-linear mixed-effects modelling will be performed given the sparse nature of the PK sampling. Appropriate PK exposure metrics will be derived from the population PK model (AUC,  $C_{min}$  and  $C_{max}$ ). The relationship between plasma investigational product levels/exposure metrics and response will be explored graphically and a formal exposure-response model may be developed.

A separate Modelling & Simulation Analysis Plan will be prepared to describe the data and methods to be used in the population PK analysis. The analysis will be performed using NONMEM v7.4 or higher version. The results of the population PK analysis will be reported separately to the CSR.

### **6.2 Efficacy Assessments**

Efficacy endpoints will include the following parameters: EEG, seizure diary and CGI-C.

## 6.2.2 Seizure Diary

The patient's legal representative (parent[s]/caregiver[s]) will be provided with a seizure diary at the Screening Period visit (Visit 1) to record the number of seizures daily starting from the day after Visit 1 until the patient discontinues the investigational product. The seizure diaries for each patient will be assessed at Screening, Day 1, Day 2 to 6, Day 7, Day 12 or 13 or 14, Day 21 and 28 of Treatment Period 1, and Day 42 of Treatment Period 2.

The investigator will ensure that the seizure diary is being completed. The investigator will also review seizure counts to ensure the number of seizures is not increasing. The seizure diaries will indicate whether spasms are still present. [REDACTED]

### 6.2.3 Clinical Global Impression of Change

The CGI-C assessment will be collected from both the investigator and the parent/caregiver on Day 1, Day 7, Day 21 and Day 28 of Treatment Period 1 and Day 42 of Treatment Period 2. The CGI-C is a validated instrument that allows the investigator to rate the change in a patient's condition on a 7-point scale ranging from "very much improved since the initiation of treatment" to "very much worse since the initiation of treatment." [REDACTED]

**Table 6-1 Clinical Global Impression of Change Scale**

Scale #	Impression
1	very much improved
2	much improved
3	minimally improved
4	no change
5	minimally worse
6	much worse
7	very much worse

## 7 STATISTICAL METHODS

### 7.1 General

All statistical analysis will be conducted following the principles specified in the International Conference on Harmonization (ICH) Topic E9 Statistical Principles for Clinical Trials (CPMP/ICH/363/96).

All statistical analyses will be performed using the statistical software SAS, Version 9.4 or newer and any exceptions will be detailed in the CSR.

All results collected in the database will be presented in listings. Both absolute values and change-from-baseline values for each subject will be given where applicable. All continuous data will be listed with the same precision as presented in the database. Data listings will be sorted by subject ID, and time point.

Unless otherwise noted, continuous variables will be summarized using the number of non-missing observations (n), arithmetic mean (mean), standard deviation (SD), median, minimum, maximum, Quartile 1 (Q1), and Quartile 3 (Q3); categorical variables will be summarized using the frequency count and the percentage of subjects in each category. Time to event data will be summarized using median, 25%, and 75% percentiles.

In the data listings, study day relative to first dose of treatment may be presented. Study day relative to first dose will be calculated as: event date – first dose date (+1 if event date  $\geq$  first dose date).

Baseline will be the last non-missing available measurement prior to first dose of the study drug.

For safety summaries, the unscheduled and repeat assessments will not be summarized; however, all results will be included in the data listings.

All PK parameters will be summarized by the overall treatment group using descriptive statistics to include, as appropriate, n, mean, SD, coefficient of variation (CV), minimum, median, maximum, geometric mean (GM), and geometric CV.

Disposition, demographics and baseline characteristics, all safety parameters and adverse events will be summarized overall.

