### 3.8.2 Clinical Laboratory Assessments

Blood and urine samples will be collected for hematology, coagulation, serum chemistry and urinalysis at the time points on Screening and Day 7, Day 28 and on Day 42.

Hematology: Hematocrit, hemoglobin, mean corpuscular hemoglobin, mean corpuscular hemoglobin concentration, mean corpuscular volume, platelet count, red blood cell count, and total and differential (absolute and percent) leukocyte count

Coagulation International normalized ratio, partial thromboplastin time, and prothrombin time

Serum Chemistry: Albumin, alanine aminotransferase, alkaline phosphatase, amylase, anion gap, aspartate aminotransferase, bicarbonate, bilirubin (total and direct), blood urea nitrogen, calcium, chloride, cholesterol (total, high-density lipoprotein, and low-density lipoprotein), creatine phosphokinase, creatinine, gamma-glutamyltransferase, globulin, glucose, lactate dehydrogenase, magnesium, phosphorus, potassium, sodium, total protein, triglycerides, and uric acid

Urinalysis: Appearance, bilirubin, color, glucose, ketones, leukocyte esterase, microscopy (performed if dipstick is positive; includes bacteria, casts, crystals, epithelial cells, red blood cells, and white blood cells), nitrites, occult blood, pH, protein, specific gravity, turbidity, and urobilinogen

Abnormal clinical laboratory values will be flagged as either high or low (or normal or abnormal) based on the reference ranges for each laboratory parameter. The investigator will determine whether any of the abnormally high or low results are clinically significant or not clinically significant. Clinical significance is defined as any variation in results that has medical relevance and may result in an alteration in medical care (e.g., active observation, diagnostic measures, or therapeutic measures). If a clinically significant change from the screening value is noted, the clinically significant value and reason for clinical significance will be documented on the AE page of the eCRF. The investigator will continue to monitor the patient with additional assessments until the value has reached the reference range, or the value at the Screening Period visit, or until the investigator determines that follow-up is no longer medically necessary.

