### 3.8.4 Electrocardiograms

The 12-lead ECG will be measured at following time points: Screening, Treatment Period 1 on Day 7 and 28, and Treatment Period 2 on Day 42.

ECG parameters will include RR interval, PR interval, QRS width, QT interval, and QT interval from Fridericia's formula (QTcF). Subjects with ECG assessments will be interpreted locally and will include comments on whether the tracings are normal or abnormal; rhythm, presence of arrhythmia or conduction defects; morphology, any evidence of myocardial infarction, or ST segment, T Wave, and U Wave abnormalities.

The investigator will determine whether any of the 12-lead ECG results are normal or abnormal, and if abnormal results are clinically significant or not clinically significant. Clinical significance

is defined as any variation in results that has medical relevance and may result in an alteration in medical care (e.g., active observation, diagnostic measures, or therapeutic measures). If a clinically significant change from screening values is noted, the clinically significant value and reason for clinical significance will be documented on the AE page of the patient's eCRF and a pediatric cardiology consultation will be prompted.

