### **7.3 Examination of Subgroups**

Additional subgroup summaries will be performed to determine whether differences exist in primary safety and efficacy endpoint results between subgroups.

The list of potential subgroups (with applicable definitions in parentheses) includes, but is not necessarily limited to, the following:

- Sex (Female vs. Male)
- Age (6-12 months; >12-24 months; >24-36 months)
- Concomitant anti-epileptic drugs (AEDs) (Specific categories to be finalized prior to database lock. The categories will be determined based upon which AEDs or combinations of AEDs the subjects take during the course of the study)

For each subgroup variable, the frequency and percentage will be displayed.

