## 7.9 Extent of Exposure

Exposure data will be presented in a listing and summarized by overall treatment.

Total exposure [mg] of a patient will be defined as the cumulative dose of study drug that a patient received during the course of the study. The extent (duration) of exposure will be derived in days as Date of last dose – Date of first dose + 1.

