## 7.12 Analysis of Safety Data

### 7.12.1 Adverse Events

All AEs will be coded to SOC and PT using Medical Dictionary for Regulatory Activities (Version 22.0 or later) and presented by subject in data listings.

A treatment-emergent adverse event (TEAE) is defined as any AE that began or worsened following the start of dosing of Treatment Period 1, Day 1 to Follow-Up.

A treatment-related AE is defined as any TEAE that is assessed by the Investigator as possibly, probably or definitely related to study drug.

Adverse event analyses will be conducted using the Safety Population.

The overall incidence of TEAEs (number and percentage of subjects) as well as the number of events will be summarized for mild TEAEs, moderate TEAEs, severe TEAEs, TEAEs assessed as at least possibly related, SAEs, TEAEs leading to study or drug discontinuation, SAEs related to study drug, life-threatening SAEs and SAEs resulting in death. All AE reports will also include the action taken as a result of the AE such as dose not changed, drug interrupted, drug withdrawn, dose increased, not applicable, or unknown.

The following TEAEs summaries will be presented (where applicable the number of patients (%)) and number of events will be summarized) by SOC and PT for overall treatment group:

- TEAEs
- Treatment-related TEAEs
- TEAEs leading to investigational product discontinuation
- Treatment-related TEAEs leading to investigational product discontinuation
- Serious TEAEs
- Treatment-related serious TEAEs
- TEAEs leading to death
- Treatment-related TEAEs leading to death.

All TEAEs will be summarized by SOC and PT using frequency counts and percentages (i.e., number and percentage of patients with an event); also the number of events will be presented

Tabulations will include an overall incidence of subjects reporting at least one AE, an overall incidence of TEAEs, and incidence within SOC and PT. Each patient may only contribute once (i.e., most severe occurrence) to each of the incidence rates, regardless of the number of occurrences.

For the incidence at the subject level by SOC, PT and relationship to study drug; if a subject experiences more than 1 event within the same SOC and PT, only the most related occurrence (in

descending order of definitely related, probably related, and possibly related) will be included in the incidence.

Listings of AEs, TEAEs, SAEs, TEAEs leading to death and TEAEs leading to study drug discontinuation will also be presented.

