## 8 TABLES, FIGURES, AND LISTINGS

Table/Figure Number	Table/Figure Name
Section 14.1	Demographic and Subject Characteristics Data Summaries
Table 14.1.1	Summary of Subject Disposition (All Enrolled Population)
Table 14.1.2	Analysis Populations (All Enrolled Population)
Table 14.1.3	Summary of Demographic and Baseline Characteristics (Safety Population)
Table 14.1.4	Summary of Medical History (Safety Population)
Table 14.1.5	Summary of Prior & Concomitant Medications (Safety Population)
Table 14.1.6	Summary of Exposure (Safety Population)
Section 14.2	Pharmacokinetic and Efficacy Data Summaries
Table 14.2.1.1	Summary of Electroencephalogram Responses (EAS Population)
Table 14.2.1.2	Summary of Electroencephalogram Responses (mEAS Population)
Table 14.2.2.1	Descriptive Summary for Time to Relapse, Resolution of Spasms and Hypsarrhythmia during Dose Tapering Period (EAS Population)
Table 14.2.2.2	Descriptive Summary for Time to Relapse, Resolution of Spasms and Hypsarrhythmia during Dose Tapering Period (mEAS Population)
Table 14.2.3.1.1	Summary of Seizure Diary Card (EAS Population)
Table 14.2.3.1.2	Summary of Seizure Diary Card (mEAS Population)
Table 14.2.3.2.1	Summary of Seizure Diary Review (EAS Population)
Table 14.2.3.2.2	Summary of Seizure Diary Review (mEAS Population)
Table 14.2.4.1	Summary of CGI-C Assessments Results (EAS Population)

---

Table 14.2.4.2	Summary of CGI-C Assessments Results (mEAS Population)
Table 14.2.5	Summary of Pharmacokinetic Plasma JBPOS0101 Concentrations (PK population)
Table 14.2.6	Summary of Pharmacokinetic Urine JBPOS0101 Concentrations (PK population)
Table 14.2.7	Summary of Urine Volume (PK population)
Figure 14.2.1	Mean (+SD) Plasma JBPOS0101 Concentrations vs Time for Day 1 (PK Population) ( Note: Present in linear and semi-log scales. )
Figure 14.2.2	Mean (+SD) Plasma JBPOS0101 Concentrations vs Time for Day 21 (PK Population) ( Note: Present in linear and semi-log scales. )
Section 14.3	Safety Data Summaries
Section 14.3.1	Displays of Adverse Events
Table 14.3.1.1	Overall Summary of Treatment-Emergent Adverse Events (Safety Population)
Table 14.3.1.2	Summary of TEAEs by System Organ Class and Preferred Term (Safety Population)
Table 14.3.1.3	Summary of Treatment-Related TEAEs by System Organ Class and Preferred Term (Safety Population)

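### TEAEs are tabulated only overall across a forced titration, taper and off-drug follow-up, and lab and ECG shift tables leave out off-schedule results; tables by dose stage and worst value would be a cheap improvement

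*SAP*

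**What the plan says.** **Adverse events.** SAP 7.1 states that "Disposition, demographics and baseline characteristics, all safety parameters and adverse events will be summarized overall". SAP 7.12.1 defines a TEAE as "any AE that began or worsened following the start of dosing of Treatment Period 1, Day 1 to Follow-Up" and presents the tables by system organ class and preferred term for the overall treatment group. SAP Section 8 lists nine TEAE tables, 14.3.1.1 to 14.3.1.9: one overall summary and eight by class and term. No title mentions dose, period or stage at onset. Protocol 7.7.1 lists the same eight summaries, also without a split.

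**Exposure.** SAP 7.9: "Total exposure [mg] of a patient will be defined as the cumulative dose of study drug that a patient received" over the study. Duration is last dose date minus first dose date plus one. Time at each dose is not summarised.

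**Subgroups.** SAP 7.3 names sex, age and concomitant anti-epileptic drugs. The list "includes, but is not necessarily limited to, the following", so a split by dose stage is not excluded, but none is planned.

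**Off-schedule results.** SAP 7.1: "For safety summaries, the unscheduled and repeat assessments will not be summarized". They remain in the listings. Labs are scheduled "at the time points on Screening and Day 7, Day 28 and on Day 42" (SAP 3.8.2), and ECGs at "Screening, Treatment Period 1 on Day 7 and 28, and Treatment Period 2 on Day 42" (SAP 3.8.4).

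**The concern.** Every patient is planned to pass through the same sequence of doses, so one pooled TEAE percentage mixes onset at 6, 9 and 15 mg/kg, during two taper steps and after stopping. Protocol 3.1.1 says the study is to provide initial safety and tolerability outcomes for future studies. Someone planning such a study would want to know whether events began on escalation, at the top dose, on withdrawal or off drug. The planned tables do not show this.

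The AE data carry particular weight at 9 mg/kg. If the Visit 3 tests precede that day's evening dose, no scheduled lab, ECG, vital-sign measurement or examination falls at 9 mg/kg, unless a patient attends for early termination. AEs and the seizure diary are then the main safety information at that dose.

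The rule on unscheduled and repeat results raises a separate question. Protocol 6.6 foresees unscheduled visits for repeat testing after abnormal labs and for AE follow-up. A patient's worst value may come from such a visit, and the shift table would then show a milder picture than the data.

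**Working it through.** **1. The plan's own figure.** Protocol 3.1 and SAP 3.1 give periods of up to 28 (screening), 28, 14 and 14 days: 28 + 28 + 14 + 14 = 84 days, as stated. The pooled TEAE window is 28 + 14 + 14 = 56 nominal days.

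**2. Stage lengths.** The dose-change days come from protocol 3.1 and SAP 3.1, with Visit 3 on Day 7, the change to 9 mg/kg at that evening's dose, and Day 42 counted as off drug.

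| Stage | Nominal span | Days | Share of 56 |
|---|---|---|---|
| 6 mg/kg | Day 1 AM to Day 7 AM, 13 doses | 6.5 | 11.6% |
| 9 mg/kg | Day 7 PM to Day 14, 15 doses | 7.5 | 13.4% |
| 15 mg/kg | Days 15-28 | 14 | 25.0% |
| First taper step (half) | Days 29-34 | 6 | 10.7% |
| Second taper step (half again) | Days 35-41 | 7 | 12.5% |
| Off drug | Days 42-56 | 15 | 26.8% |

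The sum is 56. Days after Day 28: 6 + 7 + 15 = 28, or 50%, however Day 42 is classed. Halving 15 mg/kg twice gives 7.5 and then 3.75 mg/kg, so the taper steps are different doses and should not share a row.

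**3. Two inputs the documents leave open.**
- *End of the 6 mg/kg stage.* One sentence gives 6 mg/kg for seven days (7.0 and 7.0 days for the first two stages). The next starts 9 mg/kg with the evening dose of Visit 3 (6.5 and 7.5 days).
- *Day 42.* Protocol 3.1 has the product stopped on Day 42. Protocol 6.1.5.3 puts Follow-Up (nominal Day 56) 14 days after the last dose, so the last dose would be on 56 - 14 = Day 42. If Day 42 is on drug, the second taper step is 8 days and off drug 14.

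**4. Visit windows.**
- Visit 3 on Day 5 or Day 9: 6 mg/kg lasts 4.5 or 8.5 days, and 9 mg/kg lasts 9.5 or 5.5.
- Visit 7 on Day 51 or Day 61: the share after Day 28 is 23/51 = 45.1% or 33/61 = 54.1%. The 15 mg/kg share is 14/51 = 27.5% or 14/61 = 23.0%.

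**5. What pooling hides (assumed count).** Suppose 10 of 35 patients each have one event and nobody drops out. The pooled table reads 10/35 = 28.6% in every case. Rates per 100 patient-days differ:
- all onsets at 15 mg/kg: 10/(35 x 14) = 2.04 during that stage and none elsewhere;
- all onsets off drug: 10/(35 x 15) = 1.90 during that stage and none elsewhere;
- evenly spread: 10/(35 x 56) = 0.51 throughout.

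**6. Gap without scheduled labs or ECGs.** Days strictly between Visits 3 and 5: 28 - 7 - 1 = 20. With windows: 26 - 9 - 1 = 16 to 30 - 5 - 1 = 24. Early termination excepted, any lab or ECG in that gap is off schedule and stays out of the change and shift tables.

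**7. Partial onset dates.** SAP 7.2.1 imputes the first of the month, moved to the first dose date if earlier. Assume a 30-day month with only the day missing. If the first dose was on the 1st, onset could be any of Days 1-30, which cover all three doses and the start of the taper, yet the imputed date is Day 1 (6 mg/kg). If the first dose was on the 27th, the remaining days are Days 1-4. All are at 6 mg/kg even with Visit 3 on Day 5, so the stage is known.

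**The case against.** The primary endpoint is TEAE incidence, and overall tables answer it. No objective compares doses, protocol 7.7.1 asks for no split, counts per stage will be small with about 35 patients, and dose is confounded with time on study. All of this stands. It makes the point an improvement, not an error.

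Several stronger readings are tempting, and the documents do not support them.

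- *The stage at onset cannot be recovered.* It can, for most events. Onset date and time are collected (SAP 3.8.1), study day may be shown in listings (SAP 7.1), dosing records are listed, and after Visit 3 the planned dose changes fall on fixed days. The hard cases are events around Visit 3, boundary days, partial dates and the case-by-case tapers of protocol 4.2.2.
- *No safety table separates doses.* The lab and ECG tables are by visit and do contrast Day 7 with Day 28. The gap concerns TEAEs.
- *Off-schedule abnormalities disappear.* They stay in the listings, including Table 14.3.4.1 for abnormal labs and Listing 16.2.8.5 for ECGs meeting criteria. They become AEs if judged to be clinically significant changes.
- *Leaving out a repeat always loses the worst value.* Where the abnormal value came from a scheduled visit, it is already in the tables. Only a value first found, or found to be worse, off schedule is missing.
- *Early-termination results are excluded.* That visit shares a scheduled column with Visit 6, which has labs and an ECG, and nothing excludes it.

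What remains is that a reader must place each event by hand from listings to see the pattern of the primary endpoint over the titration, and that the shift tables can miss a worst value.

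**Conclusion.** Both halves hold as cheap improvements that the sponsor should make. None of the nine TEAE tables shows the stage at onset. One window pools six stages, of which 15 mg/kg is 25% of nominal days (23.0-27.5% with the Visit 7 window), and 50% (45-54%) falls after the last full-dose day. Change and shift tables omit labs and ECGs done off schedule, notably in the 20 nominal days (16-24 with windows) between Visits 3 and 5.

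A reader might infer that the overall incidence is biased or that the SAP departs from the protocol. Neither follows: the overall figure is valid, and the protocol plans the same tables. How often an off-schedule value would be a patient's worst cannot be known from the documents.

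The percentages assume patients follow the nominal schedule to Day 56. That each TEAE table has only an overall column is read from the text and table titles, because no table shells are given.

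**What to change.** 1. **TEAEs by stage.** Add descriptive tables of TEAEs, related TEAEs, serious TEAEs and TEAEs leading to discontinuation by the stage in effect at onset or worsening: 6, 9 and 15 mg/kg, first taper step, second taper step, off drug. Give patients and patient-days at risk per stage. Derive the stage from the actual dosing record and onset date and time, including case-by-case early-withdrawal tapers, or from the dose on the AE page if captured (protocol 6.1.5.4 lists it; SAP 3.8.1 does not). Use 'stage unknown' only where a partial date does not determine the stage. State that dose is confounded with time on study and dropout.
2. **Before programming.** Reconcile the two statements on when the 6 mg/kg stage ends, and state whether Day 42 is on or off drug.
3. **Exposure.** Summarise patients and days at each stage as well as total mg and total days.
4. **Labs and ECG.** Base shift and outlier tables, including QTcF, on the worst post-baseline value, with unscheduled and repeat results included. State that the Early Termination visit counts. Keep by-visit means scheduled-only.
5. **Minor.** SAP 7.12.4 says ECGs meeting criteria will be summarised as well as listed, but Section 8 has only the listing. Add the table.

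The cost is SAP wording and a few tables from data already planned, with no new visits or samples; it adds no tests at 9 mg/kg. The downsides are small counts per stage, possible assignment of late-onset events to the wrong stage, and worst-value tables that look worse for patients tested more often.
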